5.6.3.1 CNS Symptoms Temporally Associated with ARIA-E MRI Findings

CNS symptoms temporally associated with ARIA-E are defined as onset or worsening of CNS symptom(s) that is/are temporally associated with ARIA-E MRI findings. CNS symptoms experienced by the participant that are new or worsened since the last MRI without ARIA-E are collected in a CNS Symptoms Request Form before the MRI takes place at a visit. To identify CNS symptoms temporally associated with ARIA-E MRI findings, the following definitions will be used:

NEW CNS symptoms: If there is any AE reported in the eCRF with “Reported on the MRI CNS symptoms request form” = Y that is [new since date of most recent MRI scan showing no ARIA-E findings] AND is [ongoing or ends between the date of most recent site visit prior to date of MRI scan showing new ARIA-E (MRI) and date of MRI scan showing ARIA-E resolution (MRI)] then ARIA-E should be classified as associated with CNS symptoms

OR

WORSENERD CNS symptoms: If there is any AE reported in the eCRF with “Reported on the MRI CNS symptom request form” = Y that is [started before the date of most recent MRI scan showing no ARIA-E findings] AND is [ongoing or ends between the date of

most recent site visit prior to date of MRI scan showing new ARIA-E (MRI) and date of MRI scan showing ARIA-E resolution from MRI data] AND [there is an increase in severity grading] then ARIA-E should be classified as associated with CNS symptoms.

The CNS symptoms temporally associated with ARIA-E MRI findings will be listed and summarized by treatment group and within this also by APOE ε4 genotype (number of alleles).

5.6.4 Laboratory Data

Laboratory data will be summarized by treatment group for each assessment visit using descriptive statistics of absolute values and change from baseline values. In addition, the frequency of participants with abnormal laboratory values will be summarized by treatment group.

5.6.5 Vital Signs

Vital signs assessments include systolic blood pressure, diastolic blood pressure, and pulse rate measured throughout the study. Vital sign measurements will be summarized by treatment group for each assessment visit using descriptive statistics of absolute values and change from baseline values. In addition, the frequency of participants with abnormal results will be summarized by treatment group.

5.6.6 ECGs

ECG data will be summarized by treatment group for each assessment visit using descriptive statistics of absolute values and change from baseline values for the following parameters:

- Heart rate
- QRS duration
- RR interval
- PR interval
- QT intervals (including QTcF)

For QTcF, the summary will also include 2-sided 90% confidence interval at each time-point.

In addition, ECG overall interpretations will be summarized by treatment group and visit.

5.6.7 Columbia-Suicide Severity Rating Scale (C-SSRS)

The **C-SSRS** is an assessment tool used to assess the lifetime suicidality of a participant (C-SSRS at baseline) as well as any new instances of suicidality (C-SSRS since last visit). The structured interview prompts recollection of suicidal ideation, including the intensity of the ideation, behavior, and attempts with actual or potential lethality.

Suicidal ideation, suicidal behavior, and self-injurious behavior without suicidal intent will be summarized by treatment group. In addition, change from baseline to worst post-baseline assessment in suicidality categories will be summarized by treatment group.

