- At risk for suicide in the opinion of the investigator
- Alcohol and/or substance abuse or dependence (according to the criteria specified in the Diagnostic and Statistical Manual of Mental Disorders, Version 5) within the past 2 years

Nicotine use is allowed.

Marijuana use is not allowed and must be discontinued at least 3 months before screening.

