#### **4.5.8 Columbia–Suicide Severity Rating Scale**

The C-SSRS (<http://www.cssrs.columbia.edu>) is an assessment tool used to assess the lifetime suicidality of a participant (C-SSRS at baseline) as well as any new instances of suicidality (C-SSRS since last visit). The structured interview prompts recollection of suicidal ideation, including the intensity of the ideation, behavior, and attempts with actual or potential lethality. The C-SSRS baseline will be collected at baseline and the C-SSRS since the last visit will be collected at subsequent visits as indicated in the schedule of activities (see [Appendix 1](#)).

The assessment will be completed by a certified C-SSRS rater after he or she interviews the participant and the participant's study partner during the study visit.

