### **6.5 SAFETY ANALYSES**

The safety-analysis population will include all randomized participants who receive at least one dose of study drug, with participants grouped according to the treatment actually received, as defined in the SAP.

- Incidence, nature, and severity of MRI safety findings: ARIA-E and ARIA-H
- Incidence, nature, severity, and timing of injection-site reactions
- Incidence, nature, and severity of serious adverse events
- Incidence, nature, and severity of adverse events

- Incidence of adverse events of special interest
- Incidence of treatment discontinuations due to adverse events
- Mean changes in clinical laboratory tests from baseline over time; incidence of treatment-emergent abnormal laboratory values and abnormal laboratory values reported as adverse events
- Mean change in ECG assessments from baseline over time and incidence of abnormal ECG assessments
- Physical and neurologic examination abnormalities
- Mean change in vital signs (blood pressure, pulse rate) from baseline over time and incidence of abnormal vital sign measurements
- Changes in CSSR-S scores from baseline over time
- Number and proportion of participants with ADAs during the study relative to the number and proportion of participants with ADAs at baseline

*Prior to completion of the study a separate ADA cutoff date may be established to allow expedient samples analyses and early access by third party vendors. The ADA cutoff date will be applied when there is sufficient ADA sample data available to adequately assess immunogenicity.*

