5. STATISTICAL ANALYSES

5.1 GENERAL CONSIDERATIONS

The clinical cutoff date for the primary analysis is defined by the date of the last randomized participant plus 116 weeks.

In the following sections, for all continuous variables for which descriptive statistics are indicated, the following statistics will be reported: the number of observations, the mean, median, standard deviation, and minimum and maximum. The 25th and 75th percentiles

(Q1 and Q3) will also be reported for selected tables. Descriptive summaries of discrete data will include frequencies expressed in terms of number and percentage of participants.

For clinical endpoints and biomarkers assessments, the baseline is defined as the assessment taken at the baseline visit (Day 1) up to and including the day of first study drug intake. If no assessment is reported at the baseline visit up to the day of first study drug intake, the earliest assessment reported after Day 1 and up to the day of second dose or Day 35, whichever is earlier, will be used as baseline. If no assessment is reported either at baseline visit or up to Day 35, an assessment reported at screening will be used as baseline. Day 35 is the latest timepoint allowed for Week 4 visit as per protocol.

For all other assessments, the baseline is defined as the last available assessment prior to first study drug intake, unless specified otherwise.

For biomarkers (CFS and plasma), values below the lower limit of quantification (LLOQ) will be set to $0.5 \times \text{LLOQ}$, while values above the upper limit of quantification (ULOQ) will be set to ULOQ. A summary table will be provided to summarize the values below LLOQ and above ULOQ for each treatment arm.

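### The C-SSRS change analysis sets a lifetime baseline against since-last-visit follow-up, so it cannot show new on-study suicidality as worsening in anyone with an equal or worse lifetime history

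*SAP*

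**What the plan says.** SAP 5.6.7 introduces the instrument as one "used to assess the lifetime suicidality of a participant (C-SSRS at baseline) as well as any new instances of suicidality (C-SSRS since last visit". Protocol 4.5.8 fixes which form is used when: "The C-SSRS baseline will be collected at baseline and the C-SSRS since the last visit will be collected at subsequent visits".

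SAP 5.6.7 then plans two outputs. The first is a by-arm summary: "Suicidal ideation, suicidal behavior, and self-injurious behavior without suicidal intent will be summarized by treatment group". The second, added to it, is the "change from baseline to worst post-baseline assessment in suicidality categories", also by treatment group.

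No C-SSRS-specific baseline is defined. The general rule in SAP 5.1 for assessments other than clinical endpoints and biomarkers is that "the baseline is defined as the last available assessment prior to first study drug intake, unless specified otherwise". The schedule of activities (Protocol Appendix 1, Table 1) has no C-SSRS at screening and one at Day 1, so that rule selects the lifetime form. Protocol 6.5 has a similar item, "Changes in CSSR-S scores from baseline over time", although SAP Section 1 says that the SAP wording supersedes the protocol.

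Neither document gives a recent-period C-SSRS baseline, a treatment-emergent rule for C-SSRS findings, a definition of the suicidality categories, or a derivation of change.

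**The concern.** A change from baseline is interpretable only if both ends measure the same quantity. Here one end is the worst state over a whole life and the other is the worst state over the treatment period. The difference mixes a change in the participant's condition with a change in the length of the window.

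People with a lifetime history can enroll. Protocol 4.1.2.1 excludes those "At risk for suicide in the opinion of the investigator", which concerns present risk. It also accepts past major depression when there has been no episode within a year, or when it is in remission or controlled by treatment.

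What is at stake is the readability of one descriptive safety output. It is the only C-SSRS summary described that relates on-study findings to baseline status, and in participants with a history it is insensitive to new events.

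**Working it through.** **Recall windows.** Participants are 50 to 90 years old at entry (Protocol 4.1.1), so the baseline form looks back over at least 50 years. The post-baseline C-SSRS visits are Weeks 24, 52, 76, 104 and 116 (Protocol Appendix 1, Tables 1 to 3). The successive intervals are 24, 28, 24, 28 and 12 weeks, which add up to 116 weeks.

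**Cells of the change.** The SAP does not define its categories, so I assume the ordering none (0) < ideation (1) < behavior (2). Change is the worst post-baseline category minus the lifetime baseline category.

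| Lifetime baseline | Worst on study: none | Ideation | Behavior |
|---|---|---|---|
| None | 0 | +1 | +2 |
| Ideation | −1 | 0 | +1 |
| Behavior | −2 | −1 | 0 |

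Six cells contain an on-study event (the last two columns). In three of them the change is zero or negative: ideation to ideation (0), behavior to behavior (0) and behavior to ideation (−1). None of these three can appear as worsening. In the first column, the two participants-with-history cells are negative (−1 and −2) although nothing about the participant need have improved. This result needs no assumed rate.

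**Illustration of size.** The plan states no figure to reproduce, and every input below is assumed. Let L be the proportion with a lifetime history, r0 the on-study event rate without a history and r1 the rate with one. Taking history as yes or no:

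- share of participants with on-study events who do not show as worse = L·r1 / (L·r1 + (1 − L)·r0)
- proportion of all participants who appear improved through the shorter window = L·(1 − r1)

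With r0 = 2%:

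| L | r1 | Share not shown as worse | Apparent improvement |
|---|---|---|---|
| 5% | 2% | 0.001/0.020 = 5% | 4.9% |
| 10% | 10% | 0.010/0.028 = 36% | 9.0% |
| 20% | 20% | 0.040/0.056 = 71% | 16.0% |

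The yes/no version overstates the first column of results, because lifetime ideation followed by on-study behavior would show as worse. If only a fraction q of on-study events fail to exceed the lifetime category, the share is multiplied by q. With q = 0.8, the middle row becomes 0.8 × 35.7% = 29%. The spread from 5% to 71% comes entirely from the chosen inputs and says nothing about this trial.

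**The case against.** The strongest reply is that the events are reported elsewhere. The by-arm summary comes first in SAP 5.6.7 and the change analysis is an addition to it. SAP 5.6 gives the double-blind safety analyses a window that starts on the day of first dose and runs to 14 weeks after the last dose, stopping before any open-label dose. A participant with old ideation and new ideation at Week 52 falls within that summary. This stands. A reader might infer that new suicidality would vanish from the report, and the documents do not support that.

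Second, SAP 5.6.7 does not use terms such as improved or no change, and the category ordering above is inferred. If the output is a full baseline-by-worst cross-tabulation, every event has a visible cell. SAP Section 1 places table layouts in separate documents that are not available here. This stands in part: a cross-tabulation would keep the events visible. But it cannot be presumed. SAP 5.6 describes the C-SSRS output as changes in scores and names shift tables only for laboratory data. Even in a cross-tabulation, the diagonal and lower cells would invite the wrong reading unless the recall periods are stated.

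Third, lifetime history is fixed before randomization and the same rule applies to both arms, so no bias toward either arm is expected. This stands. It does not restore sensitivity within the change table, or remove apparent improvement in both arms.

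Fourth, the baseline form might also record a recent period. The documents describe it only as lifetime. If recent-period data exist, the SAP should name them as the baseline.

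**Conclusion.** The point holds for the change analysis only. As specified, it compares a lifetime state with a since-last-visit state. It cannot show worsening for a new event at or below the lifetime category, and it shows a decrease for a history with no on-study event. The mismatch of recall periods follows from the documents. The cell-by-cell result also rests on reading the output as an ordered change.

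The consequence is limited. The analysis is descriptive and touches no hypothesis test, estimand or error rate. The separate by-arm summary should still capture the events. Two stronger readings are tempting: that a safety signal would be concealed, and that those with a history are the participants most likely to have events. The first is answered by the by-arm summary. The second is an assumption with no source in either document. The size of the loss cannot be computed, and the percentages above are illustrative only.

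**What to change.** In SAP 5.6.7, replace the change-from-baseline summary with a table of worst on-treatment category (none, ideation, behavior) by arm, cross-classified by lifetime history at baseline in the same categories. In the text or a footnote:

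- define the categories and state the two recall periods;
- count any ideation or behavior after first dose as an on-study event, whatever the lifetime history;
- exclude the Day 1 baseline form from the on-treatment column, because the SAP 5.6 window opens on the day of first dose;
- state that cells below the diagonal are not to be interpreted as improvement.

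The cost is a few lines of SAP wording and one re-specified table from data already collected. The downside is that an event continuing a recent pre-study state counts as on-study. The cross-classification keeps such participants visible in the rows with a lifetime history.

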5.7 OTHER ANALYSES

5.7.1 Summaries of Conduct of Study

The summary of study conduct will include a description of the following items by treatment arm:

- Number of participants enrolled and randomized
- Number of participants included in each analysis set
- Number and percentage of participants who prematurely withdrew from the study or from study treatment (including the reasons for discontinuation and the distribution of these discontinuations by time-windowed visit)
- Incidence of protocol deviations – overall and by four main categories (inclusion criteria, exclusion criteria, medication and procedural)
- Stratification factor reported in IxRS and used for randomization
- Number of participants with home nursing
- Number of participants initiating or changing symptomatic treatment of AD during the study

Major protocol deviations and premature withdrawals will be listed.

5.7.2 Summaries of Treatment Group Comparability

Demographics and baseline characteristics (including age, sex, medical history, randomization stratification factors) will be summarized descriptively by treatment arm as assigned for the ITT analysis set using:

- means, SDs, medians, and ranges for continuous variables
- counts and proportions for categorical variables

Exposure to AD concomitant medication (including post-baseline initiation or change in dose) will be summarized by treatment arm for the ITT analysis set.

5.7.3 Immunogenicity Analyses

Immunogenicity analyses include the evaluation for antibodies against gantenerumab, including the determination of antibody titers. The results of the confirmatory assay will be presented as a frequency table summarizing baseline and post-baseline results.

A listing of participants with positive ADA status per confirmatory assay and titer result will be provided.

5.7.4 Summaries of COVID-19 Impact on the Trials

Studies GRADUATE I and GRADUATE II were ongoing during the COVID-19 pandemic. Consequently, to monitor the potential impact of the pandemic on the trials, we will provide a specific set of descriptive analyses related to COVID-19 by treatment arm for the ITT analysis set (see [Table 2](#)), including:

- Demographic and Baseline Characteristics in Participants with Confirmed/Suspected COVID-19
- COVID-19 AEs (see Section [5.6.2](#))
- COVID-19 related Protocol Deviations
- Missed doses due to COVID-19
- Study discontinuations due to COVID-19 as determined by the adjudication committee for ICEs
- Study drug administrations of 1020 mg Q4W
- Remote scale administrations
- Duration of study site closure

5.7.5 Amyloid PET Substudy

The objective of the GRADUATE I and GRADUATE II longitudinal amyloid PET substudies is to assess changes in brain amyloid load over time using the change in florbetaben or flutemetamol from baseline to the last amyloid PET visit in the Standard Uptake Value Ratio (SUVR).

Two amyloid PET ligands are allowed in the GRADUATE I and GRADUATE II longitudinal amyloid PET substudies to provide assessment of β -amyloid protein deposition according to country and site availability: radiopharmaceuticals florbetaben-F18 and flutemetamol-F18. However, the same ligand has to be used for the same participant throughout the study (e.g., if a participant has been enrolled in the main study with a positive florbetaben PET scan, only florbetaben will be allowed and used for the longitudinal follow-up scans for the participant).

Centiloid mapping will be completed for SUVR data from the two amyloid PET ligands. The primary amyloid PET outcome measure is the change in amyloid PET Centiloid from baseline to Week 116.

5.7.5.1 General considerations on Amyloid PET statistical analyses

With the Centiloid endpoint, data from both tracers will be pooled and analyzed together. Separate analysis by tracer with the Centiloid endpoint may also be conducted as appropriate. When SUVR metrics is the endpoint, the analysis will be done separately and reported separately for each tracer, when possible.

Missing values will not be imputed.

The amyloid PET analyses will be performed on the Amyloid-PET-mITT analysis set (see [Table 2](#)), unless otherwise specified, and participants will be analyzed according to the treatment assigned at randomization by IxRS.

5.7.5.2 Summaries of Treatment Group Comparability

Demographics and baseline characteristics (including age, sex, medical history, randomization stratification factors) will be summarized descriptively by treatment arm as assigned for both the Amyloid-PET-mITT analysis set and the Amyloid-PET-longitudinal analysis set (see [Table 2](#)) using:

- means, SDs, medians, and ranges for continuous variables
- counts and proportions for categorical variables

5.7.5.3 Visit Windowing

For amyloid PET assessments, due to the long time between scheduled assessments, time windows based on study days, as defined in [Table 7](#), will be used. Study days are defined based on days on study since the date of the first dose, with the day of the first dose being study day 1.

Table 7 Time Windows for Amyloid PET Assessments

| Visit | Target day | Time window |
|----------|------------|--------------|
| Baseline | 1 | Up to day 35 |
| Week 52 | 365 | 281, 449 |
| Week 116 | 813 | 645, 897 |

For Week 116, the time window will cover the week 104 timepoint as well. In case of more than one assessment within a time window, the assessment with the date closest to the target day is selected. For the combined window of Week 104 and 116, the target day is the Week 116 assessment day.

Because of visit windowing, data collected at an early termination visit will be summarized at the corresponding visit as defined by the time window. For participants who have discontinued treatment early, if a PET scan is performed more than 56 days (early termination visit expected 14 days after last dose, followed by time window per protocol for early termination is ± 42 days) after the date of last dose, the PET scan will not be used for the analysis.

The end of a substudy is defined as the date when all participants enrolled in the substudy have:

1. completed the last required amyloid PET scan (Week 116), or
2. completed an early termination scan, or
3. discontinued from the main study.

5.7.5.4 Definition of the Estimand for Amyloid PET

The scientific question of interest for the amyloid PET substudies is to assess the effect of the intended study treatment on the PD endpoint, change from baseline in amyloid load burden at Week 116, in the absence of a substantial impact of the COVID-19 pandemic and as if treatment discontinuation would not have occurred.

The primary Amyloid PET estimand is thus described by the following attributes:

- **Target Population:**
Early (prodromal to mild) AD population as identified by the inclusion and exclusion criteria, see Sections 4.1.1 and 4.1.2 of the substudy protocols and Sections 4.1.1 and 4.1.2 of the main study protocols
- **Variable:**
Change from baseline to Week 116 in amyloid PET Centiloid
- **Treatment:**
Prescribed study drug including up-titration to the target dose
- **Population-level summary:**
Difference in variable means between treatment arms
- Intercurrent events
 - Substantial reduction in drug exposure due to the COVID-19 pandemic (defined as ≥ 4 missed dose-months)
 - Treatment discontinuation due to any reason

Amyloid PET is listed in the protocol under “Pharmacodynamic Biomarker Objective”. Considering that Amyloid PET primarily aims at estimating the Pharmacodynamic effect of the drug, rather than a direct measure of clinical efficacy, reporting treatment effect estimated “as if there were no treatment discontinuations and no substantial reduction in exposure due to COVID-19 pandemic” (thus using a hypothetical strategy) addresses the scientific question of interest.

Details for Definition of Variable

The Centiloid variable will be used rather than the original SUVR, because it allows to combine data from different tracers, by mapping SUVR values to a standardized scale. The Centiloid variable is the current common standard in the scientific community.

The primary SUVR measure of interest is computed using a weighted composite target region and whole cerebellum as reference region. The weighted composite target region is composed of (both left and right side):

- frontal lobe,
- parietal lobe,
- temporal lobe lateral,

- cingulum posterior and
- anterior cingulate gyrus

Each region is weighted by its own volume. The Centiloid conversion is a linear transformation of SUVR with tracer-specific parameters that are given below:

Centiloid Equation:

$$CL = \text{SlopeCL} \times \text{SUVR} + \text{InterceptCL}$$

CL= Centiloids; SlopeCL= slope; SUVR= standard uptake value ratio of the target region; InterceptCL= intercept.

The pertinent values for the two tracers are:

Table 8 Primary Centiloid Equation Parameters

| Tracer | Reference | Slope | Intercept |
|------------------|------------------|-------|-----------|
| Florbetaben-F18 | whole cerebellum | 175.6 | -174.2 |
| Flutemetamol-F18 | whole cerebellum | 143.5 | -141.1 |

